the studies were done using not validated assessment tools, different types of steroids, administration routes and dosages. Steroids have potentially severe side effects, especially on prolonged use including immunosuppression, osteoporosis, Cushing's syndrome, myopathy, and hyperglycemia. Some of these effects can be particularly serious in patients with advanced cancer. Therefore it is important to better determine the symptomatic effects relative to the potential side effects of these drugs. None of studies described the underlying mechanism of action of steroids on symptoms.

In recent years, it has become evident that many cytokines have powerful effects on the brain. Animal models of symptoms such as pain and cachexia, and clinical studies of immunotherapy in which pro-inflammatory cytokines are administered to patients with various cancers have provided important insight into the central effects of these agents. Sickness behavior is typically associated with behavioral changes seen in humans and laboratory animals suffering from microbial infections and includes symptoms of cognitive dysfunction, anxiety, psychomotor slowing, fatigue, anorexia, sleep alterations and increased sensitivity to pain. Relevant to their mediation by cytokines, symptoms of sickness behavior can be reliably reproduced in both laboratory animals and humans by administration of each of the cytokines that induce the pro-inflammatory cytokine cascade (TNF- α , IL-1, IL-6). The cytokines and pro inflammatory mediators are elevated in advanced cancer patients, are associated with these symptoms. Dexamethasone and other steroids could potentially decrease the symptoms specifically, fatigue, nausea, anorexia and pain by decreasing these cytokines and inflammatory substances.

At present, the association between the effects of dexamethasone on symptoms and its effects in decreasing cytokines and inflammatory substances has not been established using validated assessment instruments and laboratory correlates in a randomized controlled trial. Our study will be the first to provide an association. By linking symptomatic response to dexamethasone with the circulating cytokines we will be able to better establish the role of cytokines in the frequency and severity of symptoms. The finding in the study will help in development of cytokine specific suppressive therapies that could be used to prevent and treat these troubling symptoms.

Selected Research Areas

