10.4 Study Design

We will conduct a prospective, randomized, double blind, placebo controlled study comparing Dexamethasone 4mg orally two times per day for 14 days versus placebo. 100 Eligible patients who agree to participate in the study and provide written informed consent will be randomized to either group A, in which patients will receive Dexamethasone orally, 4mg two times a day for 14 days; or group B, in which patients will receive placebo orally, two times a day for 14 days. On day 15, all patients will be receive 4mg of dexamethasone twice a day on a open label basis till Day 21,From Day 22 to Day28 the dose of dexamethasone is to be tapered to 2mg orally twice a day. Subsequently patients will be off study with dose tapered to the minimum tolerated dose. All study patients will be asked to return to the clinic for follow-up assessments 2 weeks after the study medication is discontinued (day 43 ± 3 days) for a safety and toxicity assessment. The reason to have open label design after Day15 is to observe the descriptive trends.

Exam (including history including FACIT-F, FAACT, HADS, ESAS, BPI, physical exam and toxicity assessment will be done day 0(baseline), Day 8 [\pm 3], Day 15[\pm 3], Day 22[\pm 3], Day 29[\pm 3]. GSE on days 8 [\pm 3], 22[\pm 3] and 29[\pm 3]. Patients will also be assessed by the research nurses for any signs and symptoms of infection while on the study drug. Laboratory correlates including cytokine levels- IL-1, IL-6, TNF- α , IL-10, IL-8, activated monocytes and corresponding receptor levels, complete blood counts, chemistry (electrolytes), C-reactive protein on day 0(baseline), Day 8, Day 15, Day 22, Day 29. The ESAS and Toxicity evaluation on Day 4 would be done through the phone.

A subset of ten patients will be asked to complete the Pittsburg Sleep Quality Index at baseline and Day 15 [\pm 3]. These patients will also collect saliva cortisol specimens at baseline and Day 15 [\pm 3]. We will select the subset of 10 patients sequentially. Every patient will be approached regarding the optional procedure of participating in the quality of sleep questionnaires and the cortisol levels, We will collect the pilot data on the first 10 patients that consent.

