Recently, simultaneous measurement of multiple cytokines with a small sample size is made possible with the use of Luminex method. We have examined the levels of multiple cytokines in plasma of chemo-naïve patients with sarcoma. As shown figure 3 below, the preliminary results of these assays in a cohort of 8 patients showed that prior to treatment with chemotherapy, a number of endogenous cytokines are measurable in the plasma of these cancer patients. After one cycle of chemotherapy, there is a marked decrease in the levels of Th-1 type of cytokines such as IL-2, IFN-gamma, and TNFalpha. In contrast, the levels of IL-6, IL-8 and IL-10 were increased. We also examined the levels of IL-6 by ELISA to see if there was a correlation in the levels. As shown in the fig. 3 below, IL-6 levels were increased post treatment by both Luminex and ELISA methods. We plan to further examine the correlation between symptom distress experienced by these patients and the circulating levels of cytokines as patients undergo cytotoxic treatment. In the present proposal, we wish to examine the cytokine profile before the initiation of treatment with Dexamethasone and during treatment and at the end of the study with Dexamethasone vs. placebo, and sought correlation between the cytokine levels, symptom clusters, and response to Dexamethasone treatment.

E. Research design and Methods.

We will conduct a prospective, randomized, double blind, placebo controlled study comparing Dexamethasone 4mg orally two times per day for 14 days versus placebo. Eligible patients who agree to participate in the study and provide written informed consent will be randomized to either group A, in which patients will receive Dexamethasone orally, 4mg two times a day for 14 days; or group B, in which patients will receive placebo orally, two times a day for 14 days. On day 15, all patients will be receive 4mg of dexamethasone twice a day on a open label basis till Day 21,From Day 22 to Day28 the dose of dexamethasone is to be tapered to 2mg orally twice a day. Subsequently patients would be off study with dose tapered to the minimum tolerated dose.

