The reason to have open label design after Day15 is to observe the descriptive trends. Exam (including history including FACIT-F, FAACT, HADS, ESAS, BPI, GSE (on days 8, 22, and 29), physical exam and toxicity assessment will be done day 0(baseline), Day 8 [± 3 days], Day 15 [± 3 days], Day 22 [± 3 days] Day 29 [± 3 days]. ESAS and Toxicity will be done on day 4. A physician will do a physical exam on the patient on day 0, 15, and Day 29; and the nurse will do a nursing assessment on days 8, and day 22. If patient is unable to return to clinic on Day 8, 15, 22, or 29 the assessments will be done by the research nurse by phone. Laboratory correlates including cytokine levels- IL-1, IL-6, TNF- α , IL-10, IL-8, activated monocytes and corresponding receptor levels, C-reactive protein, complete blood counts, chemistry (electrolytes) within 7 days of baseline, Day 8 [\pm 3 days], Day 15 [± 3 days], Day 22 [± 3 days], and Day 29 [± 3 days]. If patients are unable to return to clinic on Day 8, 15, 22, or 29 the laboratory correlates will not be done. Patients will also be assessed by the research nurses for any signs and symptoms of infection while on the study drug. All study patients will be asked to return to the clinic for follow-up assessments 2 weeks after the study medication is discontinued (day 43 ± 3 days) for a safety and toxicity assessment. If the patient is unable to return to the clinic on day 43, the safety and toxicity assessment will be done by the research nurse by telephone.

The electrolytes measured will include chloride (Cl), carbon dioxide (CO2), Potassium (K) and Sodium (Na).

Treatment plan is illustrated in Figure 2.

Figure 2.

2005-0816 April 5, 2011

| | | | - | | | | Page 30 of 60 |
|----------------|----------|-----|-------|-------|-------|-------------|---------------|
| Assessments | Baseline | Day | Day 8 | Day | Day | Day 29 | Dăy 43 [± 3 |
| | | 4+ | [± 3 | 15[± | 22 | [± 3 days] | days] |
| | | | days | 3 | [±3 | | |
| | | | | davs] | days] | | |
| MDAS | Х | | | | | | |
| | | | | | | | |
| BPI | Х | | Х | Х | Х | Х | |
| FACIT-F | Х | | Х | Х | Х | Х | |
| FAACT | Х | | Х | Х | Х | Х | |
| HADS | Х | | Х | Х | Х | Х | |
| r-ESAS | Х | Y | Х | Х | Х | Х | PE or Y |
| GSE | | | Х | | Х | Х | |
| Toxicity | Х | Y | Х | Х | Х | Х | PE or Y |
| Demographics | Х | | | | | | |
| Cytokine, | Within 7 | | Х | Х | Х | Х | |
| Activated | days | | | | | | |
| monocytes | - | | | | | | |
| and | | | | | | | |

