| corresponding | | | | | | | |
| receptor | | | | | | | |
| levels | | | | | | | |
| C-reactive | Within 7 | | Х | Х | Х | Х | |
| protein | days | | | | | | |
| Electrolytes | Within 7 | | Х | Х | Х | Х | |
| (CI, CO2, K, & | days | | | | | | |
| Na), CBC | | | | | | | |
| MD physical | PE | | | PE | | PE | |
| exam | | | | | | | |
| RN | | | Α | | Α | | |
| assessment | | | | | | | |

X = assessment, Y=phone evaluation, PE= MD assessment, A= RN assessment

Table. 1 Clinical and Laboratory Evaluation During Study

Recruitment

H. Screening Measures

Symptom clusters and intensity: Patient must have 3 or more symptoms (fatigue, Pain, nausea, anorexia/cachexia, sleep problems, depression) based on Edmonton Symptom Assessment System, and the average intensity of each symptom during last 24 hours must be >/= 4 on a 0 to 10 scale (0 is no symptom, 10 is worst possible symptom). Target symptoms chosen for this study were based on previous research by our group and others, suggesting that Dexamethasone has potential effects on these symptoms. According to NCCN guideline, symptoms such as pain and fatigue are measured on a 0 to 10 numerical scale (0 is no symptom, 10 is worst symptom imaginable) can also be measured on categorical scale, none (0), Mild (1-3), Moderate (4-6) and Severe (7-10). We will include patients with symptom intensity >/= 4 (moderate or severe).

Clinical setting

Patients will be recruited from the Palliative Care and Rehabilitation Medicine, Pain center, and Thoracic center at M.D. Anderson Cancer Center. Patients will also be

recruited from LBJ hospital and at Four Seasons Hospice in Flat Rock, North Carolina. The physicians will identify potential eligible patients to participate in this study.

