6. The most serious side effects known with dexamethasone is Cardiovascular: Edema, hypertension, arrhythmias, cardiomyopathy, myocardial rupture (post-MI), syncope, thromboembolism, thrombophlebitis, vasculitis. Central nervous system: Insomnia, nervousness, vertigo, seizures, psychosis, pseudotumor cerebri (usually following discontinuation), headache, mood swings, delirium, hallucinations, euphoria. Dermatologic: Hirsutism, acne, skin atrophy, bruising, hyperpigmentation, pruritus (generalized), perianal pruritus (following I.V. injection), urticaria.Endocrine & metabolic: Diabetes mellitus, adrenal suppression, hyperlipidemia, Cushing's syndrome, pituitary-adrenal axis suppression, growth suppression, glucose intolerance, gynecomastia, hypokalemia, alkalosis, amenorrhea, sodium and water retention, hyperglycemia, hypercalciuria, weight gain. Gastrointestinal: Appetite increased, indigestion, peptic ulcer, nausea, vomiting, abdominal distention, ulcerative esophagitis, pancreatitis, intestinal perforation. Genitourinary: Altered (increased or decreased) spermatogenesis. Hematologic: Transient leukocytosis. Hepatic: Transaminases increased, hepatomegaly. Neuromuscular & skeletal: Arthralgia, muscle weakness, osteoporosis, fractures, myopathy (particularly in conjunction with neuromuscular disease or neuromuscular blocking agents), tendon rupture, vertebral compression fractures, neuropathy, neuritis, parasthesia. Ocular: Cataracts, glaucoma, exophthalmos, intraocular pressure increased. Miscellaneous: Infections, anaphylactoid reaction, anaphylaxis, angioedema, avascular necrosis, secondary malignancy, Kaposi's sarcoma, intractable hiccups, impaired wound healing, abnormal fat deposition, moon face, Topical:<1%; Itching, drvness, folliculitis, hypertrichosis, acneiform eruptions, hypopigmentation, perioral dermatitis, allergic contact dermatitis, skin maceration, skin atrophy, striae, miliaria, local burning, irritation. secondary infection

8. We will maintain confidentiality by assigning a study number to all study subjects. Data collected will be identified and tracked using this number. No names or other identifying information will be attached to the data collection.

Benefits: Several potential benefits may result. The study may provide data that will help us further understanding of symptom clusters, pro inflammatory mediators and symptom management.

Inclusion of women and minority

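### No glucose test is listed at any visit, although hyperglycemia is a named dexamethasone risk and diabetes is excluded by history only, so asymptomatic hyperglycemia would be missed unless routine care finds it

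*Combined protocol and SAP*

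**What the plan says.** **Laboratory schedule.** Section 10.4 (Study Design) schedules "complete blood counts, chemistry (electrolytes), C-reactive protein on day 0(baseline), Day 8, Day 15, Day 22, Day 29". Section E defines the chemistry: "The electrolytes measured will include chloride (Cl), carbon dioxide (CO2), Potassium (K) and Sodium (Na". The table titled "Table. 1 Clinical and Laboratory Evaluation During Study" repeats the same four analytes with a CBC, at baseline (within 7 days) and days 8, 15, 22 and 29. If a visit is handled by phone there is no blood: "If patients are unable to return to clinic on Day 8, 15, 22, or 29 the laboratory correlates will not be done".

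**Named risks.** The opening general summary ends its list of steroid effects with "myopathy, and hyperglycemia. Some of these effects can be particularly serious in patients with advanced cancer". The earlier part of that sentence ties these effects particularly to prolonged use. Protection of Human Subjects, item 6, includes "sodium and water retention, hyperglycemia, hypercalciuria, weight gain", and also diabetes mellitus and glucose intolerance. The section on adverse experiences associated with the intervention again lists diabetes and reduced carbohydrate tolerance.

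**Eligibility.** Exclusion Criteria item 7 excludes known diabetes, with no test attached. In the same list, anemia (hemoglobin below 9) and neutropenia (ANC below 1500) carry laboratory limits.

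**Toxicity capture.** Other Assessments describes a side-effect sheet based on the NCI toxicity criteria. Table 1 has toxicity assessed at baseline and days 4, 8, 15, 22, 29 and 43; day 4 is by phone ("ESAS and Toxicity will be done on day 4"). Statistical Considerations does not expect toxicity in either arm, but plans to summarize and monitor it, including at the interim look.

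**End of the controlled period.** "On day 15, all patients will be receive 4mg of dexamethasone twice a day on a open label basis till Day 21".

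**The concern.** Hyperglycemia without symptoms is found by measuring glucose. A toxicity sheet can grade it only if somebody has a value to enter, and nothing in the schedule supplies one.

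Two things are at stake.

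- **Patient safety.** A patient with undiagnosed diabetes could start dexamethasone at 8 mg a day without any glucose test required by the protocol. This applies to the placebo arm too, from day 15.
- **Reading of the toxicity summary.** Baseline to day 15 is the only placebo-controlled window. A low hyperglycemia count there could be taken as reassurance when it partly reflects lack of testing. The opening summary gives the weighing of symptom benefit against steroid side effects as one reason for doing the trial, so the count is likely to be read.

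**Working it through.** No figure in the plan is in dispute. The check is mainly a comparison of texts, with some arithmetic on what is affected and what an amendment can still reach.

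1. **The plan's sample size, to confirm that it does not depend on this point.** Inputs from Statistical Considerations: difference 7, SD 13.95, one-sided 0.05, 80% power.
   - n per arm = 2 × (1.645 + 0.842)² × (13.95/7)² = 2 × 6.185 × 3.971 = 49.1, so 50.
   - With 37% dropout: 50/0.63 = 79.4, so 80 per arm and 160 in total.
   - Both figures reproduce, and no laboratory safety measure enters either.

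2. **Is glucose measured anywhere?**
   - Section 10.4: blood count, chemistry (given as electrolytes), C-reactive protein and the cytokine panel.
   - Section E: Cl, CO2, K and Na named.
   - Table 1: the same four, plus CBC.
   - Eligibility: diabetes by history, with no glucose or HbA1c.
   - The three laboratory listings agree. No glucose, HbA1c, metabolic panel or urine glucose appears in the supplied text.

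3. **How can a case reach the record?** Through symptoms reported at a toxicity assessment, or through a glucose value obtained in routine care. An asymptomatic case with no routine test has no path.

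4. **Direction of the error.** Suppose a fraction c of true cases is recorded in each arm. The observed risk difference is then c × (p_dex − p_placebo), so it shrinks in proportion. The documents give neither c nor the rates. The figures below rest on assumed rates and show only how the shrinkage works, with 5% assumed on placebo:

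| Assumed true rate on dexamethasone | Difference at c = 1 | c = 0.5 | c = 0.25 |
|---|---|---|---|
| 15% | 10 points | 5 | 2.5 |
| 20% | 15 points | 7.5 | 3.75 |
| 30% | 25 points | 12.5 | 6.25 |

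5. **What an amendment can still reach.** Missing Data reports 43 dropouts among 115 patients, and enrolment is capped at 160.
   - Already entered: at least 115/160 = 71.9%.
   - Still to enter: at most 160 − 115 = 45, or 28.1%. That is about 22 per arm (45/2 = 22.5).
   - With dropout of 43/115 = 37.4%: 45 × 0.626 = 28.2, or about 14 per arm.
   - With zero events, the exact one-sided 95% upper limit is 1 − 0.05^(1/n): 12.7% for n = 22 and 19.3% for n = 14. These two limits describe how little the remedy can estimate. They do not measure the gap itself.
   - Patients still on study at the time of an amendment could have glucose at later draws, so 72% is the share entered earlier, not necessarily the share never tested.

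**The case against.** The strongest case on the other side has five parts.

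- **The risk is not shown to be material here.** The opening summary links hyperglycemia especially to prolonged use. Blinded dosing lasts 14 days, and scheduled dosing runs to day 28 with a step down. The other lists name it among dozens of unranked effects. This stands. The documents establish that the risk is recognized, not how common it is at this dose and duration.
- **No stated objective fails.** The aims concern fatigue, pain, anorexia, nausea, cytokines, sleep and cortisol. No hyperglycemia rate by arm is promised. This also stands, and it keeps the point among the cheap improvements.
- **Safeguards exist.** Known diabetes is excluded, toxicity is assessed at baseline and six later times, a physician examines patients at baseline and days 15 and 29, and the DMC and IRB review adverse events. A reader might infer that hyperglycemia would go unrecorded altogether. The documents do not support that, because symptomatic and incidental cases have a route onto the sheet. What remains is asymptomatic hyperglycemia not found in routine care, and undiagnosed diabetes.
- **Some material is not visible.** The recording sheet is not in the supplied text, and section E says which electrolytes are included without saying that nothing else is run. The safe statement is therefore that no glucose test is listed. A line for hyperglycemia on the sheet would still not schedule a measurement.
- **It is late.** Most patients have been entered, and a new numeric exclusion would change the eligible population mid-trial, using a limit the documents do not supply. This is right, and the fix below does not ask for one.

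**Conclusion.** The gap is real and narrow. Following the plan as written, asymptomatic hyperglycemia on dexamethasone 8 mg a day is recorded only if routine care happens to find it, and this includes the only placebo-controlled window. Any recorded hyperglycemia count is therefore incomplete and probably low, by an amount the documents do not allow anyone to estimate.

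Two stronger readings are tempting. One is that the trial's efficacy result is compromised; it is not, because the fatigue comparison and the sample size do not use these data. The other is that adding glucose now would yield a sound rate by arm; it would not, because at least 115 of up to 160 patients (72%) were entered under the present schedule. The gain is a safety check for the remaining patients and a report that states what was measured.

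The conclusion assumes that the supplied methods section and Table 1 give the full laboratory schedule, and that the 115 patients in Missing Data had all been entered by this version.

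**What to change.** 1. For the remaining patients, add serum glucose to the blood already drawn at baseline and days 8, 15, 22 and 29. The investigator reviews the baseline value before the first dose and the later values as a safety check. Do not add a mandatory numeric exclusion limit mid-trial.
2. Summarize glucose by arm through day 15, descriptively, with the number sampled and whether each sample was fasting or random. Use only draws taken before the first open-label dose; the day 15 visit has a window of ±3 days, so some draws may come after it. Show days 22 and 29 separately as open label.
3. State in the report that glucose was not systematically measured in patients entered before the amendment, so that a low hyperglycemia count is not read as evidence of safety. This is worth doing even if no amendment is made.

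**Cost.** One extra assay per draw with no extra blood sampling visit, and investigator review of the values. It needs a mid-trial amendment, which must also go to the hospice site's own IRB. Most values will be random, and there will be none at phone visits.

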- 7. Patients on topical, or inhaled corticosteroids are eligible for study. If patients have been on oral corticosteroids for </= 7 days prior to inclusion of study they are eligible for study.
- 8. Patients currently taking Megestrol must be off drug for > 7 days prior to study inclusion

Exclusion Criteria.

- 1. Allergy to Dexamethasone,
- 2. Inability to complete the baseline assessment forms
- 3. Patients currently taking Megestrol, and not off drug for > 7 days

- 4. Anemia as defined as a hemoglobin of < 9
- 5. Known history of HIV
- 6. Neutropenia as defined by an absolute neutrophil count (ANC) of < 1500 cells/mm
- 7. Patients with a history of diabetes will be excluded.
- 8. All major surgeries such as thoracotomy etc., that requires wound healing within last 2 weeks.
- 9. Those who are currently receiving oral corticosteroid therapy or who have been on corticosteroid therapy >/= 8 days prior to study inclusion
- 10. Sepsis and/or acute, chronic, or ongoing infections

Randomization

Patients will be randomized to one of two treatment arms. One arm would have 50 eligible patients and would receive Dexamethasone and another would also have 50 eligible patients will receive matching placebo. The randomization schema will be based on parameters input into RANLST, a randomization program developed at MDACC and supported by an NCI grant. A randomization list containing order information for both arms will be made. Patient names in sequence will be recorded on each list as the patients are entered and both lists will match patient name and identification number. Only the primary statistician and Investigational Pharmacy will know the complete list of the order of randomization into the two arms until the end of the study. However, the code for an individual patient as to drug treatment group may be disclosed early and the patient removed from the study in the case of a request by the primary treating physician due to adverse events. Otherwise, no other persons will know about the assignment of patients to treatment arms until the end of the study.

Outcome measures

Specific aim #1: To determine the effect of Dexamethasone on the intensity of Fatigue We hypothesize that dexamethasone decreases the intensity of symptoms namely Fatigue, nausea, anorexia and pain that occur frequently in advanced cancer as compared with those receiving placebo

1. Measures of Fatigue

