Measures of pain : Brief Pain Inventory (BPI) Pain severity and pain interference will measured with the BPI. The patient will rate symptom scores at baseline, day 8 [± 3 days], day 15 [± 3 days], day 22 [± 3 days], and day 29 [± 3 days]. The BPI asks patients to rate their pain for the last week on 0-10 scales at its "worst," "least," "average," and "now." The scales are presented in a 10 cm line, with each number equidistant from the next. Each scale is bounded by the words "no pain" at 0 end and "pain as bad as you can imagine" at the other. Using the same type of scales, patients are also asked to rate how their pain interferes with several quality of life domains including activity, walking, mood, sleep, work, and relations with others. These scales are bounded by "does not interfere" at the 0 end and "interferes completely" at the other. Patients are also asked to estimate the pain relief they are receiving from their pain treatment (in percent), to locate areas of pain on a human figure, and to estimate the cause of their pain (cancer disease, cancer treatment, or non-cancer). Issues of the validity and reliability of the BPI have been examined in detail [126,127].

Measure of anorexia: Symptom Measure (Cachexia/ Anorexia): Functional Assessment of Anorexia/Cachexia Therapy (FAACT). The patient will rate symptom scores at baseline, day 8 [\pm 3 days], day 15 [\pm 3 days], day 22 [\pm 3 days], and day 29 [\pm 3 days]. This 12 item Symptom-specific subscales in addition to FACIT-G is to measure patients additional concerns about their anorexia /cachexia. The FAACT has internal consistency and a reliability coefficient (Cronbach's alpha) of 0.88 for its 12 components [125]. Patients rate the intensity of anorexia/cachexia and its related symptoms on 0 to 4 numerical scales from 0 "not at all" to 4 "very much".

Measure of anorexia: the ESAS tool that was used for the measurement of fatigue also measures nausea.

Specific aim # 3: To determine the changes in cytokines (IL-1, IL-6, TNF- α , IL-10, IL-8, activated monocytes and corresponding receptor levels) and C-reactive protein before and after treatment with dexamethasone.

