- 2. The proposed clinical trial will enroll patients. The inclusion criteria include the following: patients present with 3 or more symptoms (pain, fatigue, appetite (anorexia/cachexia), and nausea) during the preceding 24 hours, have an average intensity ≥4 on a 0 to 10 scale, in which 0=no symptom, and 10=the worst possible symptom;; have no clinical evidence of cognitive failure, have normal Memorial Delirium Assessment Scale [MDAS] 13 or > is considered as normal); must be 18 years or older; have life expectancy ≥ 6 weeks; have a negative pregnancy test if women with childbearing potential; must understand and sign written informed consent; have no concurrent steroids or be off steroids for at least 7 days prior to inclusion into study; Exclusion criteria include patients have major contraindication to Dexamethasone, i.e. allergic reaction; are not able to complete the baseline assessment forms and are pregnant or lactating.
- 3. Data collected for the clinical trial will be from patient medical charts, assessment tools and laboratory results. Data will be collected specifically for this research purposes, and existing data from medical charts will be incorporated (i.e., demographic data).
- 4. Patients will be informed that refusing to participate in the study or deciding to terminate their participation will not affect their current treatment plan. The patients will be given a written and verbal description of the study during the informed consent teaching interview. Guidelines regarding Institutional Review Board, Human Rights Protection will be strictly followed.
- 5. Study subjects will sign an IRB-approved written informed consent form after having the study explained to them in person by the physician. Included in this explanation will be a reassurance that lack of participation in the study will not bear a relationship to their care for cancer or its symptoms. Circumstances of obtaining informed consent will be documented in patient medical records. Informed consent will be obtained in the language preference of the potential subject. When necessary, professional translators, and not family members, will obtain written informed consent.

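### The corticosteroid eligibility rule is stated three ways that do not agree, so patients just off a short oral course can enter with steroid-affected baseline values

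*Combined protocol and SAP*

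**What the plan says.** The rule appears in two sections of the combined protocol and SAP.

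- **Eligibility Requirements, Inclusion Criterion 7.** On oral use: "If patients have been on oral corticosteroids for </= 7 days prior to inclusion of study they are eligible for study". On other routes: "Patients on topical, or inhaled corticosteroids are eligible for study". No stop date and no interval off drug is given.
- **Eligibility Requirements, Exclusion Criterion 9.** It bars "Those who are currently receiving oral corticosteroid therapy or who have been on corticosteroid therapy", the second group with a cut-off of 8 days or more before inclusion. No look-back limit is given.
- **Protection of Human Subjects, item 2.** In its summary of the inclusion criteria, patients must "have no concurrent steroids or be off steroids for at least 7 days prior to inclusion into study". No route is named.

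Three other parts of the plan bear on the consequence. Specific aim 3 concerns change in cytokines "and C-reactive protein before and after treatment with dexamethasone". Research design and Methods (section E) lets the baseline laboratory sample, cytokines included, be drawn within a window: "chemistry (electrolytes) within 7 days of baseline". The background section on corticosteroids and symptoms states that dexamethasone lowers several of the cytokines to be measured, among them IL-1, IL-6 and IL-8.

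**The concern.** The study drug is itself a corticosteroid, so this criterion decides whether a patient's baseline is free of the drug class under test. If the texts give different answers for the same patient, the enrolled population depends on which text the screener follows.

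If a recently exposed patient is admitted, the baseline fatigue score and cytokine levels may already reflect steroid treatment. The change from baseline then does not run from an untreated state. In the placebo arm, such a patient may also be going through steroid withdrawal or losing a residual benefit during the blinded phase.

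**Working it through.** No arithmetic applies. No figure in the plan rests on the steroid rule: the 50 evaluable patients per group follow from 7 points, SD 13.95, one-sided 0.05 and 80% power whichever text is used. The check is to put test patients through the three statements.

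| Patient | Inclusion 7 | Exclusion 9 | Human Subjects item 2 |
|---|---|---|---|
| On day 5 of an oral course, still taking it | Fits | Barred (current use) | Not met |
| 5-day oral course ended yesterday | Fits | Not barred, if 8 days means course length | 7 days off not met; met only if being off drug today is enough |
| 3-week oral course ended a month ago | Silent | Barred as written, since there is no look-back limit | Met |
| Current inhaled or topical user | Eligible | Current-use clause covers oral only | Not met on its face, since no route is named |

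**Can the texts be reconciled by reading?** There are two ways to read the day counts.

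1. As course length. Inclusion 7 then allows a course of up to 7 days and Exclusion 9 bars one of 8 days or more. The two cut-offs meet without a gap. Two things remain. Inclusion 7 is worded so that it covers a course still running, which Exclusion 9 bars. And neither criterion contains the 7-day interval off drug found in the Human Subjects text.
2. As time before entry. Exposure in the last 7 days would be allowed and exposure 8 or more days back would be barred. That is the reverse of an interval off drug and contradicts the Human Subjects text outright.

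Course length is the more workable reading, and it still leaves the second patient in the table admitted by the eligibility lists with no time off drug required.

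**What follows for baseline.** For that patient the fatigue score is taken within days of steroid use. The laboratory sample may precede baseline by up to 7 days, so it can fall inside the steroid course. On the plan's own premise about cytokines, the pre-treatment value is then not an untreated one.

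**What follows for the comparisons.** The within-patient cytokine change, and the correlations of symptom change with cytokine change, use that baseline directly. For the primary test of fatigue change from baseline to day 15, randomization balances prior exposure between arms in expectation. No stratification by prior steroid is stated, so chance imbalance is possible. Exposed patients given dexamethasone continue with the class; those given placebo stop it.

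**Can affected patients be identified later?** The baseline variables listed under Other Assessments are age, gender, education, race, ethnicity and cancer diagnosis. Steroid history is not among them.

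**The case against.** Much can be said for the plan.

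- **Current users are screened out.** Meeting an inclusion criterion does not cancel an exclusion. The monitoring section says every participant is registered in one system that accepts only patients who meet all criteria. This stands: with both lists applied, a patient still on oral steroid does not enter. A reader might infer that patients are randomized while taking an oral steroid, or that the sites are enrolling different populations. The documents support neither. The checklist itself is not shown, however, and the hospice site lies outside the lead centre's monitoring teams, so consistent use of one reading cannot be confirmed.
- **The 7- and 8-day cut-offs are complementary.** This stands in part, as shown in the working.
- **The Human Subjects text is a loose summary.** It also departs from the eligibility list on life expectancy (6 weeks against 30 days), the direction of the MDAS cut-off, the symptom list and pregnancy. That is true, and it calls for the whole summary to be brought into line. It does not settle which steroid rule applies.
- **Randomization protects the comparison.** This stands for allocation bias, and the plan also compares cytokine change between the randomized arms. It does not restore an untreated pre-treatment value.
- **The entry threshold helps.** Patients need at least three symptoms at 4 or more out of 10, which removes some whose symptoms are controlled by steroid. Fatigue need not be one of the three.

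A reader might also infer a definite loss of power by assuming that some share of patients contributes no treatment contrast. The documents give no exposure share. The assumption does not follow either: a patient just off a steroid and then given 14 days of dexamethasone or placebo still differs by assigned treatment, and withdrawal on placebo would widen the contrast.

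**Conclusion.** The eligibility rule is wrong as written: it is an internal inconsistency in current text. The certain part is textual. A current short-course user, a patient just off a short course, a patient with a long course well in the past, and an inhaled or topical user can each get different answers depending on the statement applied or how it is read.

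The consequence is narrower. Followed as written, the eligibility lists can admit patients with recent, stopped oral exposure. The cytokine objective is the most directly affected. For the primary comparison the effect is added noise and possible carry-over or withdrawal. Neither its size nor its direction can be worked out, because the documents give no exposure share, no time since last dose and no size of residual effect. That recent exposure occurs at all is plausible rather than shown: the plan describes corticosteroids as widely used for these symptoms, admits some patients on intravenous chemotherapy, and describes dexamethasone as an antiemetic for chemotherapy.

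**What to change.** 1. Reconcile the three statements into one rule that specifies route, duration of use and time since last dose. Use the same words in the eligibility list, the registration checklist and the human-subjects section. Which rule is right is a clinical decision for the sponsor, and none is proposed here.
2. Record drug, dose and last-dose date of recent steroid use at baseline. The missing-data section already reports dropout among 115 patients, so the same items would have to be taken from medical charts for those enrolled, before unblinding.
3. Pre-specify one sensitivity analysis of the primary endpoint and of the cytokine changes that excludes recently exposed patients, with recent exposure defined in advance.

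The cost is amendment wording, a short addition to the baseline case report form, chart abstraction for patients already entered, and one further analysis. The sample size calculation does not change.
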